7.6.2 Analyses of Pharmacokinetic Parameters

7.6.3 Analyses of Pharmacokinetic Parameters for Stage 1

Summary of PK parameters for each dose level will be presented in terms of n, mean, SD, CV%, median, minimum, maximum, geometric mean, and geometric CV%. Geometric mean and geometric CV% will only be calculated for AUC and Cmax. Individual derived PK parameters will also be listed by dose level.

7.6.4 Analyses of Pharmacokinetic Parameters for Stage 2

No PK parameters will be derived.

7.7 Analysis of Pharmacodynamics Data

Generally speaking, for Stage 1 and Stage 2, the summaries will be provided for active treatment ENT-01 or by dose level if deemed as necessary. The comparison is made to baseline for each PD variable up to the end of fixed dosing period plus washout period.

For Randomized population of Stage 2, the descriptive summaries will be provided for active treatment and placebo. Due to small sample size resulting from amended protocol, there will be no formal statistical comparisons between active treatment and placebo for PD variables.

7.7.1 Analysis of Continuous Pharmacodynamics Data

The following continuous PD parameters and their change from baseline will be summarized by period (run-in [baseline], dosing periods (diary) or treatment period (questionnaire data), and washout) for each appropriate population, using descriptive statistics as specified in Section 7.1 (General Statistical Procedures).

Stool Diary PD parameters:

- CSBM days per week
- CSBM episodes per week (Stage 2 only)
- SBM days per week
- SBM episodes per week (Stage 2 only)
- Average ease of passage
- Average stool consistency
- Days using rescue meds per week
- Number of rescue meds use per week

Sleep Diary PD parameters:

- Total sleep time (hours) per day
- Delay (minutes) in sleep onset per night
- Total awake time (hours) per night
- Number of wakes per night
- Number of arm or leg thrashing days per week

Questionnaire PD parameters:

- Total score from NMSQ
- Total score from BDI-II
- Total score from MMSE
- Total score from UM-PDHQ
- Total scores from PFS-16
- Total score and 3 subdomain scores from PAC-SYM
- Total Score and 4 subdomain scores from PAC-QoL
- Total Score from RBDQ
- Total score and Part I to III scores from UPDRS

7.7.2 Analysis of Categorical Pharmacodynamics Data

The following categorical PD parameters will be summarized by period (run-in [baseline], dosing periods [diary] or treatment period [questionnaire data], and washout) for each

appropriate population, using frequency distribution as specified in Section 7.1 (General Statistical Procedures).

Stool Diary PD parameters:

- Stage 1 CSBM based on dosing day diary
- Stage 1 SBM based on dosing day diary
- Success based on CSBM days per week (Stage 2 only) - primary efficacy outcome variable
 - The proportion of subjects for whom the drug was a success at the end of fixed period will be estimated with a binomial point estimate and corresponding 95% confidence interval. The observed proportion of successes will be compared to 0.10 using an exact binomial test. Success will be defined as an increase in CSBM/week of 1 or more OR a CSBM/week of 3 or more.

Sleep Diary PD parameters:

- Disappearance of arm or leg thrashing (Yes/no)

Questionnaire PD parameters:

- BDI-II Depression categories

7.8 Analysis of Safety Data

7.8.1 Adverse Events

Adverse events will be coded into SOC and PT using the current version of MedDRA. Severity of AEs will be assessed by investigators according to CTCAE (v4.03). In database, Grade 1 is labeled as Mild, Grade 2 as Moderate, and Grade 3 as Severe.

AEs that have a possible, probable or definite relationship to study drug will be defined to be related to the study drug while others will be defined as “not related”. AEs with the closest relationship to the study drug will be used for summary.

The number and percentage of subjects who experienced an AE during escalation and fixed dosing periods will be summarized by dose level (Stage 1: 75 mg up 200 mg; Stage 2: 75 mg up to 250 mg, fixed dose, and washout) and overall for each stage and for the Safety population. The denominator for calculating the percentages will be based on the number of subjects ever exposed to each dose and overall in the Safety Population.

Additionally, the number and percentage of subjects who experienced an AE during randomization period will be summarized by treatment (Placebo and ENT-01). The denominators for calculating the percentages will be based on the number of subjects ever exposed to each treatment in the Randomized Population.

A treatment emergent adverse event (TEAE) is defined as adverse events with a date of onset (or worsening) on or after the start date of a treatment up to the start date of the next treatment. The following types of summaries will be provided:

- Overview of TEAEs
- TEAEs by SOC and PT
- TEAEs by SOC, PT, and Maximum CTCAE toxicity grade
- TEAEs by SOC, PT, and Maximum CTCAE toxicity grade ≥ 3
- TEAEs by SOC, PT, and closest relationship to study drug
- TEAEs by PT in decreasing frequency
- Drug-related TEAEs by SOC and PT
- Drug-related TEAEs by PT in decreasing frequency
- Serious TEAEs by SOC and PT
- TEAEs leading to study discontinuation by SOC and PT
- TEAEs of special interest including nausea, diarrhea, and dizziness by SOC and PT.

If a preferred term or system organ class was reported more than once for a subject, the subject would only be counted once in the incidence for that preferred term or system organ class.

In tabulation by severity (i.e., CTCAE toxicity grade),

- For a given preferred term, only the most severe preferred term for each subject will be included.
- For a given system organ class, only the most severe system organ class for each subject will be included.

Similarly, in tabulation by relationship,

- For a given preferred term, the most closely related preferred term to the study drug for each subject will be included.
- For a given system organ class, the most closely related system organ class to the study drug for each subject will be included.

Adverse events including baseline AEs, serious adverse events, and adverse events leading to discontinuation from the study will be provided in separate data listings.

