PK subjects will come to the site on Day 1 of randomization ON AN EMPTY STOMACH and return their unused study drug at that time point. They will receive the first dose of medication at the site following the first PK blood draw, and complete the questionnaires listed below. PKs will also be performed at 1, 2, 4, and 8 hours post-dose. A sample for liver function tests will be drawn with the 8-hour post-dose PK draw. They will receive 4 daily doses to take home, then return on Day 6 to receive their 6th dose at the site after their first PK draw of the day. PKs will again be obtained post-dose at 1, 2, 4 and 8 hours, a sample for liver function tests will be drawn with the 8-hour post-dose PK draw, and all the questionnaires completed.

Following the 5-7 day course on the pro-kinetic dose, ALL patients will be randomized to drug or placebo and enter Period 4. Randomization will be 1:1 to treatment vs. placebo. Randomization will occur in accordance with the randomization schedule generated by [name] at Weill-Cornell Medical College. Patients and study staff will be blinded to actual study treatment and will remain blinded throughout the remainder of the study. BDI, MMSE, Trail making A and B, NMSQ, UM-PDHQ, PFS-16, RBDQ, PDSS, PAC-SYM and PAC-QOL will be administered prior to randomization. The UPDRS will be administered and weight and vital signs will be taken).

Assuming randomization is to treatment group, the patient will remain on that dose daily for a 6 day period (6 dosing days). Patients randomized to placebo will be switched to the same number of placebo tablets as they were taking prior to switching. All patients will continue to keep daily diaries during this period. The use of rescue medication (suppositories and enemas) for constipation will be permitted as needed if a bowel movement has not occurred for 3 days and recorded in the diary. Patients will be contacted daily. The suppository will be taken on the evening of the third day as shown in Figure 1 above. *Any bowel movement produced as a result of rescue medication will not be counted.*

Patients reaching their tolerability limit at a dose lower than a clinically effective dose (STDE) will be terminated from the study. We have included 40 patients in this Stage to allow for 15% drop-outs for reasons including tolerability.

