An assessment of normal or abnormal will be recorded and if the EKG is considered abnormal, the abnormality will be documented on the CRF. EKGs will be repeated if clinically significant abnormalities are observed or artifacts are present.

Laboratory Assessments

Laboratory assessment samples are to be obtained at designated visits as detailed in the Schedule of Procedures and Assessments.

All clinically significant laboratory values should be captured on the CRF as AEs.

Blood and urine samples will be analyzed at the laboratory facility at the Investigational site. Urine samples will be analyzed by dipstick, and a microscopic analysis will be performed if the results of dipstick indicate abnormalities to be further investigated. All laboratory reports must be reviewed, signed, and dated by the Investigator. A legible copy of all reports must be filed with both the patient's CRF and medical record (source document) for that visit. Any laboratory test result considered by the Investigator to be clinically significant should be considered an AE (clinically significant AEs include those that require an intervention). Clinically significant abnormal values occurring during the study will be followed until repeat test results return to normal, stabilize, or are no longer clinically significant.

Adverse events

All reported AEs will be coded using the CTCAE version 4.03 terminology. The incidence of treatment-emergent AEs (TEAEs; events with onset dates on or after the start of the study drug) and treatment-related AEs will be summarized by system organ class (SOC) and preferred term

(PT). Events with missing onset dates will be included as treatment-emergent. If a patient experiences more than 1 occurrence of the same AE, the occurrence with the greatest severity and the closest association with the study drug will be used in the summary tables. SAEs and AEs that result in treatment discontinuation will be summarized. In addition, AEs of special interest will be summarized by SOC and PT; categories of AEs of special interest include: nausea, vomiting, abdominal pain, diarrhea, and rectal bleeding.

All AEs will be listed by patient, along with information regarding onset, duration, relationship and severity to study drug, action taken with study drug, treatment of event, and outcome.

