6.2 Safety Population

For each stage, safety Population will consist of all subjects who receive at least one dose of ENT-01 during that stage.

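### SAP 7.8.1 leaves the randomized-period events of ENT-01 patients out of the Stage 2 overall adverse-event rate; separately, its special-interest list omits three protocol terms without saying so

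*SAP*

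**What the plan says.** SAP 7.8.1 sets up two adverse-event displays for Stage 2.

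- **Safety Population table.** "The number and percentage of subjects who experienced an AE during escalation and fixed dosing periods will be summarized by dose level", with the Stage 2 columns given as "Stage 2: 75 mg up to 250 mg, fixed dose, and washout", and an overall column. The overall denominator comes from SAP 6.2: "safety Population will consist of all subjects who receive at least one dose of ENT-01 during that stage".
- **By-arm table.** "Additionally, the number and percentage of subjects who experienced an AE during randomization period will be summarized by treatment", with Placebo and ENT-01 as columns and the Randomized Population as denominator.

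The dose does not change at randomization for the active arm. Protocol 3.1 (Period 4) says: "Assuming randomization is to treatment group, the patient will remain on that dose daily for a 6 day period (6 dosing days"; SAP 2.3 agrees. Protocol 10.5 asks for Stage 2 adverse events by dose level and at each person's individual effective dose (LSTDEi), with no restriction by period.

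On adverse events of special interest (AESIs), Protocol 10.3.1 says: "categories of AEs of special interest include: nausea, vomiting, abdominal pain, diarrhea, and rectal bleeding". SAP 7.8.1 says: "TEAEs of special interest including nausea, diarrhea, and dizziness by SOC and PT".

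**The concern.** A column labelled overall for Stage 2 should cover all ENT-01 exposure in that stage. As worded, it takes in washout, when patients are off drug, but not the randomized days on which the ENT-01 arm is still taking the drug at an unchanged dose. Those patients are in the denominator throughout. Any patient whose first event of a given term falls in those 6 days is then counted as event-free for that term. In the grade and relationship tables, the same happens to a worst or most closely related event that falls there. Safety and tolerability of repeated doses is a primary objective of Stage 2 (Protocol 2.2, SAP 3.2.1), so this rate will be read as a main result.

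The AESI list is a second, independent matter. Protocol 1.3 puts the main safety focus on local gastrointestinal effects, yet three gastrointestinal terms named in the protocol are not named in the SAP list.

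**Working it through.** **1. The plan's own exposure figure.** Inputs under the 27 July 2017 protocol: dose levels 75 to 175 mg in 25 mg steps, which is 5 levels (SAP 2.1); 3 dosing days per level; 2 to 4 further fixed-dose days (Protocol 3.1, Period 3.2); 6 randomized days (Period 4).

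Longest course: 5 × 3 + 4 + 6 = 25 days. This reproduces the 25-day Stage 2 maximum in Protocol 11.

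Shortest course (response at the first level): 3 + 2 + 6 = 11 days.

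**2. Share of dosing days outside the overall column, for a patient randomized to ENT-01.** Share = 6 / (escalation days + fixed-dose days + 6).

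- Shortest course: 6/11 = 55%.
- Longest course: 6/25 = 24%.

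**3. Effect on the overall rate (illustration only).** The documents give neither the number randomized to ENT-01 nor any adverse-event rate. Assume a constant daily hazard *h* of a first event, *D* ENT-01 days before randomization, *m* patients randomized to ENT-01 and *N* = 40 in the Safety Population (the planned enrolment). Then

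understatement = (*m*/*N*) × [exp(−*hD*) − exp(−*h*(*D* + 6))].

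Example: *m* = 10, *D* = 5, *h* = 0.10 gives (10/40) × (0.607 − 0.333) = 6.8 percentage points.

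Percentage points, for *h* from 0.01 to 0.10 per day:

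| *m* | *D* = 5 | *D* = 19 |
|---|---|---|
| 5 | 0.7 to 3.4 | 0.6 to 1.3 |
| 10 | 1.4 to 6.8 | 1.2 to 2.5 |
| 20 (full planned arm, a ceiling) | 2.8 to 13.7 | 2.4 to 5.0 |

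SAP 1 and 7.7 describe the randomized sample as too small for comparison, so the last row is an upper limit and not an expectation.

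**4. AESI lists side by side.**

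| Term | Protocol 10.3.1 | SAP 7.8.1 |
|---|---|---|
| Nausea | yes | yes |
| Diarrhea | yes | yes |
| Vomiting | yes | not named |
| Abdominal pain | yes | not named |
| Rectal bleeding | yes | not named |
| Dizziness | not named | yes |

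Three of five protocol terms are not named and one is added. The change does not appear in the SAP's list of reasons for amendment (SAP 1). SAP 5.1 declares no changes from the protocol, and SAP 9 covers only two dropped secondary analyses of success.

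**The case against.** **The split is deliberate and consistent.** SAP 7.8.2 to 7.8.6 also separate the time up to the end of fixed dosing from the randomized period, and keeping open-label titration apart from blinded, placebo-controlled data is reasonable. This stands as a case for keeping the by-arm table. It does not justify an overall column whose denominator includes patients part of whose on-drug time is left out.

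**Nothing is lost.** A reader might infer that on-drug events, including serious ones, vanish from the report. They do not: they are in the by-arm table, and SAP 7.8.1 lists adverse events, serious events and discontinuations. What is missing is a pooled rate.

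**Few patients are affected.** The February 2018 amendment removed randomization, and in SAP Table 4 Period 4 is the fixed-dose period, which the overall column already counts. Only the ENT-01 arm randomized under the July 2017 protocol is concerned. This stands.

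**24% to 55% is not a bias in the rate.** It is tempting to read it so. It is a share of one patient's dosing days, and each patient counts once per term. Nor is the randomized period shown to be the longest continuous exposure: Protocol 3.1 already gives 5 to 7 consecutive days at the effective dose before randomization, against 6 in the period itself.

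**The AESI gap may be one of wording.** The SAP list is introduced as inclusive and may not be exhaustive. All three terms remain in the tables by system organ class and preferred term, and vomiting and abdominal pain that meet the dose-limiting definition are also summarized under SAP 7.8.6. It would be wrong to infer that the AESI list lowers the overall rate, or that the terms go unreported. The February 2018 amendment is also not among the documents. SAP 2.1 says it changed only the dose range and the randomization, but Table 4 shows other differences (a Day 28 call, no Sitzmarks capsules), so its AESI text cannot be checked. What remains is that the SAP departs from the July 2017 protocol without saying so.

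**Conclusion.** The point holds on the wording of SAP 7.8.1. The Stage 2 overall rate can be understated, because events on randomized ENT-01 days are outside its numerator while those patients are in its denominator, and no other table covers all Stage 2 ENT-01 exposure. Protocol 10.5 does not call for that restriction.

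For an affected patient, 24% to 55% of ENT-01 dosing days are left out. The change in the reported rate is unknown. With 5 to 10 affected patients out of 40 and the assumed hazards, it would be about 0.6 to 6.8 percentage points; all of those inputs are assumptions. The conclusion rests on taking the sentence literally. The sentence is already loose, since it lists a washout column that lies outside the two periods it names, so the authors may have meant more than they wrote.

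The AESI mismatch is a separate and smaller inconsistency. It concerns a targeted display and leaves the overall rate untouched.

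**What to change.** In SAP 7.8.1:

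1. Define Stage 2 *overall* as all ENT-01 exposure in the stage, including the randomized days of patients assigned to ENT-01, and count those days in the matching dose-level and fixed-dose columns too.
2. Keep the Placebo/ENT-01 table as an additional display.
3. Footnote the washout column: for patients randomized to placebo, washout starts only after six placebo days, so at least 6 days after their last ENT-01 dose.
4. Add vomiting, abdominal pain and rectal bleeding to the AESI table and keep dizziness, or declare and justify the shorter list in SAP 9. Either way, state a closed list.

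The cost is SAP wording and table programming. No new data are needed, and trial conduct does not change.

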Participants will receive a phone call and be asked about adverse events. They will also provide their daily stool chart to assess the severity of the constipation and use of laxatives, softeners, bulking agents and suppositories. *Patients with two or fewer complete, spontaneous bowel movements will qualify for the treatment period. A bowel movement occurring within 24 hours of suppository, softener, bulking agent or enema use will NOT be counted. A spontaneous stool is a stool occurring in the absence of a laxative, softener, bulking agent or suppository.* PAC-SYM and PAC-QOL to be administrated on day 14, or at the clinic at Dose 1 visit the following day if they fail to bring the completed survey.

PERIOD 2.1 (Stage 1): Single dose

Safety, tolerability and pharmacokinetics of orally administered single-dose ENT-01 in Sentinel Group

Duration: 22-57 days

The 10 patients in the sentinel group will be assigned to Cohort 1 and will participate in 8 single dosing periods.

Subjects	D1	D4-8	D7-15	D10-22	D13-29	D16-36	D19-43	D22-50	D25-57
1-2	25mg	50mg	75mg	100mg	125mg	150mg	175mg	200mg	
3-4		25mg	50mg	75mg	100mg	125mg	150mg	175mg	200mg
5-6		25mg	50mg	75mg	100mg	125mg	150mg	175mg	200mg
7-8		25mg	50mg	75mg	100mg	125mg	150mg	175mg	200mg
9-10		25mg	50mg	75mg	100mg	125mg	150mg	175mg	200mg

All 10 patients will be pre-selected in advance of check-in for their first scheduled dosing period. All laxatives, suppositories, softeners, bulking agents and enemas will be disallowed during the 24-hour period before or after the administration of study medication. Patients will wear the I-Button continuously for the entire dosing period. The first two patients (subjects 1-2) will first be admitted and given a single dose. The study will be conducted at a hospital-based clinical unit and patients will be monitored for 24 hours after the dose. Unless there are any safety

concerns, patients will be released at this time and brought back for the next dosing on Day 4-8 (D4-8), after a minimum of a 72 hour observation period. Dopamine will be taken prior to the clinic visit on an empty stomach. Patients will self-administer the study medication during their clinic visit. The dose will be taken on an empty stomach along with 8 oz. of water after baseline observations in the clinic. The patient will not be allowed to ingest any food for at least 60 minutes after study medication.

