therapeutic effect. Should there be more than 1 patient with AE grade 4 or 5 that is at least possibly

related to ENT-01 for doses less than 200 mg, the study will be put on an immediate safety hold

until an emergency DSMB meeting can be held to evaluate the study for possible discontinuation.

Dose-finding: Beyond the safety and tolerability, this Period will allow us to determine the dose

which is safe and tolerable in all 10 patients (STD) and which has a pro-kinetic effect in at least

some patients (STDE: Safe and Tolerable dose in all and pro-kinetic Effect in at least some). We

will start Period 3 with the STDE.

PERIOD 2.2 (Stage 1): Washout

Duration: 2 weeks

Patients will be observed off study drug and adverse events will be recorded. They will

continue to keep a daily diary throughout the period. They will continue to wear the I-Button for

five 24 hour periods between Days 1 and 5. During the second week, they will be restarted on all

original medications but will continue their diaries until the termination of the study. They will be

seen prior to study termination and BDI, MMSE, Trail making A and B, NMSQ, UM-PDHQ, PFS-

16, RBDQ, PDSS, PAQ-SYM and PAC-QOL will be administered.

Visit 2: Day 14

Patients will be reviewed prior to discharge and any adverse events noted.

DSMB review of Stage 1: The DSMB will determine whether to proceed to Stage 2.

PERIOD 3.1 (Stage 2a)

Run-in period for Cohort 2 (n=40)

Duration: 2 weeks

Conducted at home.

28

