9.13 Reporting Requirements

Any adverse event, including both observed or volunteered problems, complaints, or symptoms that begins any time between the start of the first dose and within 30 days after the end of the last dose are to be recorded briefly on the appropriate case report form and in detail in the source documents. A check list of adverse events may not be used during this study.

The following are specific definitions that are relevant to meeting your reporting obligations and which are included in the FDA Regulations, 21CFR Part 312.32, and International Conference on Harmonization of Technical Requirements for Registration of Pharmaceuticals for Human Use (ICH) Guidelines:

Adverse Event: Any untoward medical occurrence in a patient administered a pharmaceutical product and which does not necessarily have to have a causal relationship with this treatment. An adverse event can be any unfavorable sign (including an abnormal laboratory finding), symptom, or disease temporally associated with the use of the investigational drug, whether or not considered related to the investigational drug.

Serious Adverse Event: An untoward event or reaction that at any dose:

- results in death
- is life-threatening
- requires inpatient hospitalization
- prolongs existing hospitalization
- results in permanent or significant disability or incapacity
- is a congenital anomaly/birth defect
- requires intervention to prevent permanent impairment/damage

Life-threatening: An event which a patient was at risk of death at the time of event.

There is a distinction between the severity and the seriousness of an adverse event. Severe is a measurement of intensity, thus a severe reaction is not necessarily a serious adverse event. For example, a headache may be severe in intensity, but would not be serious unless it met one of the criteria for serious adverse events listed previously.

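### SAP 7.8.1 does not say where Stage 1 washout adverse events go; read literally, the last dose has 2 to 4.7 times the time at risk of lower doses, which can look like a dose effect

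*SAP*

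**What the plan says.** SAP 7.8.1 ties a treatment-emergent event to a treatment if its onset falls "on or after the start date of a treatment up to the start date of the next treatment". It gives no closing date for a treatment that has no successor. The protocol's own definitions (9.10 and 10.3.1) give a start for treatment emergence but no end.

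The same section says that subjects "who experienced an AE during escalation and fixed dosing periods will be summarized by dose level", and lists the levels as "Stage 1: 75 mg up 200 mg; Stage 2: 75 mg up to 250 mg, fixed dose, and washout". Washout appears for Stage 2 only. The denominator is "the number of subjects ever exposed to each dose", so days at risk play no part.

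In Stage 1, single ascending doses are given to each patient. Under Period 2.1 in protocol section 3.1, a patient is "brought back for the next dosing on Day 4-8 (D4-8), after a minimum of a 72 hour observation period". Period 2.2 then follows for two weeks: "Patients will be observed off study drug and adverse events will be recorded". In its second week the patients go back on their usual medications.

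**The concern.** Every Stage 1 dose except the last has a window that closes when the next dose is given. For the last dose nothing closes it, so on the literal definition all washout events are charged to that dose. They include events in the week when other drugs are restarted. Because doses only go up, the last dose is also the patient's highest. A longer window at the top, with a denominator that ignores its length, raises the percentage there even if the drug does nothing.

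The table's introductory sentence pulls the other way. If its reference to the escalation and fixed dosing periods governs, Stage 1 washout events belong to no column. One reading inflates the top dose and the other drops events from the table. Safety and tolerability of single doses is the primary objective of Stage 1, so the by-dose table should not depend on which sentence a programmer follows.

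**Working it through.** **Dosing interval.** The schedule under Period 2.1 can be rebuilt by putting visit k on Day 1 + 3k to Day 1 + 7k, for k = 0 to 8. This gives Day 1, 4-8, 7-15, 10-22, 13-29, 16-36, 19-43, 22-50 and 25-57, which matches the protocol's table. The window at every dose but the last is therefore 3 to 7 days.

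**Last window.** The Stage 1 washout is two weeks (protocol Period 2.2; SAP 2.1), so the literal window after the last dose is about 14 days.

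**Ratio of time at risk.** 14/7 = 2.0 and 14/3 = 4.7.

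**Effect on percentages.** The documents give no adverse event rate. Assume a constant rate h per patient-day that does not depend on dose. Then P(at least one event in d days) = 1 - exp(-h × d).

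| h per day (assumed) | 3 days | 7 days | 14 days |
|---|---|---|---|
| 0.01 | 3% | 7% | 13% |
| 0.03 | 9% | 19% | 34% |
| 0.05 | 14% | 30% | 50% |

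For example, at h = 0.03: 1 - exp(-0.09) = 0.09, 1 - exp(-0.21) = 0.19 and 1 - exp(-0.42) = 0.34. Of ten patients, about 3.4 would have an event at the last dose against 0.9 to 1.9 at a lower one, with no dose effect.

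**How often the table would mislead.** A simulation with no dose effect took ten patients at each of the six levels from 75 to 200 mg, treated the levels as independent, and ran 200,000 trials per setting. All ten were assumed to reach 200 mg. The chance that 200 mg shows strictly the highest percentage was:

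| h per day (assumed) | 7-day gaps, 14-day last window | 3-day gaps, 14-day last window | Equal windows |
|---|---|---|---|
| 0.01 | 25% | 42% | 8-9% |
| 0.02 | 34% | 60% | 8-10% |
| 0.05 | 48% | 84% | 10-11% |

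**Comparison with the rest of the SAP.** Laboratory results (7.8.2) and ECG findings (7.8.4) are summarised with washout as its own period. For Stage 1 stool diaries, SAP 4.4 credits one day after the final dose to that dose. For sleep diaries it credits seven days, and the next seven count as washout. Only the adverse event table has no rule for this stretch of time.

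**The case against.** The strongest reply is that the sentence setting up the table confines it to the escalation and fixed dosing periods, and Stage 1 washout is a separate period, 2.2. On that wording washout events never reach the 200 mg column and no false signal arises. This stands as a possible reading, so the bias is not certain. It does not settle the matter. It conflicts with the definition of a treatment-emergent event in the same section, and the same sentence leads into a list that includes washout for Stage 2. It would also leave Stage 1 washout events with no place in the table.

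The column list is loosely written. It starts Stage 1 at 75 mg although dosing starts at 25 mg, so the missing washout column may be an oversight. That is a further reason to correct the list.

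A reader might infer that every patient has at least 14 days after the last dose. The documents do not support that. A patient with a DLT is terminated (protocol 3.1, individual stopping criteria) and attends an early discontinuation visit if possible (4.5). No 14-day washout is assured, and that patient carries the open window at a lower dose, which weakens the contrast with 200 mg.

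A reader might also put the last window at 30 days, ten times the shortest gap, because protocol 9.13 records events "within 30 days after the end of the last dose". Protocol 9.14, however, collects events only up to the follow-up contact, and the Stage 1 schedule shows no contact after the two-week washout. The schedule supports 14 days.

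Finally, investigators' causality judgements feed separate drug-related tables, and events are listed by patient with onset (protocol 10.3.1). With ten patients, a careful reader could see late onset in the listings. That limits the damage but does not correct the summary tables.

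**Conclusion.** The concern holds as a defect in the attribution rule for the by-dose tables of treatment-emergent events. On the literal definition, a Stage 1 patient who completes washout has about 14 days at risk at the last dose against 3 to 7 days at lower doses, a ratio of 2 to 4.7. At an assumed dose-independent rate of 0.03 per day (range 0.01 to 0.05) that means 34% (13 to 50%) with an event against 9 to 19% (3 to 30%). The distortion is clearest at 200 mg, where no one has a further dose to close the window. On the other reading, Stage 1 washout events are missing from the table. The text needs one rule either way. The ratio follows from the documents; the percentages rest on the assumed rate and on its being constant over time.

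It would go too far to infer that the Stage 1 tolerability result or the choice of dose is compromised. The symptom DLTs are limited to 24 hours after dosing (protocol 9.8; SAP 4.3) and are summarised separately (SAP 7.8.6). Safety is reviewed with the DSMB before each dose level. The Stage 1 safety hold counts related grade 4 or 5 events at doses below 200 mg, so events charged to 200 mg do not enter it. These decisions are largely unaffected.

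**What to change.** In SAP 7.8.1:

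- Add a washout column for Stage 1, as Stage 2 already has, and align the introductory sentence with the definition of a treatment-emergent event.
- Apply one attribution window to every Stage 1 dose, including the last: the earlier of the next dose or a fixed number of days that is the same for all doses. If that number is no longer than the shortest gap of three days, the planned windows are equal.
- Report later events, both between doses and after the last dose, in a separate late or washout column so that none are lost.
- Show patient-days at risk, or events per patient-day, beside each by-dose percentage.
- While the list is open, reconcile its Stage 1 starting level with the 25 mg at which dosing begins.

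The common window matters. Closing only the last dose at three days, while lower doses keep up to seven, would reverse the bias: about 9% at the top against 19% below at the assumed 0.03 per day. That would understate the highest dose.

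The cost is SAP wording, a revised attribution rule for Stage 1 and extra table columns. No new data and no change in conduct are needed. Some late events leave the dose columns, but they stay visible in the late or washout column and in the overall column.
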